Visit 12: Week 70 (Month 16)	491	428-546
Visit 13: Week 86 (Month 20)	603	547-665
Visit 14: Week 104 (Month 24)	729	666-791
Visit 15: Week 122 (Month 28)	855	792-917
Visit 16: Week 140 (Month 32)	[contact]
Visit 17: Week 156 (Month 36)	1093	1037-1155
Visit 18: Week 174 (Month 40)	1219	1156-1281
Visit 19: Week 192 (Month 44)	1345	1282-1400
Visit 20: Week 208 (Month 48)	1457	1401-Open ended

* Study days = measurement date – Day 1 (date of first dose of randomized study medication) + 1

Appendix 1.2. Further Definition of Endpoints

The specific criteria for clinical endpoint definitions outlined below, and the source documentation necessary to qualify for the adjudication and confirmation of a clinical endpoint event, are described in the Adjudication Committee Charter.

Cardiovascular Death

Cardiovascular death is defined as sudden cardiac death, fatal myocardial infarction (MI), death due to heart failure, death due to stroke (fatal ischemic stroke or fatal stroke of undetermined etiology), or death due to other cardiovascular causes.

Myocardial Infarction

The MI categories contributing to the MI endpoints for this study are those defined in the Third Universal Definition of Myocardial Infarction, as Type 1 (plaque rupture with thrombus), Type 2, (MI due to an ischemic imbalance, ie, an increase in oxygen demand or a decrease in oxygen supply resulting in cardiac injury), Type 3 (MI resulting in cardiac death, when symptoms of ischemia, or ECG evidence of ischemia are present, but death occurred before biomarkers could be obtained), Type 4 (MI related to PCI [Type 4a], stent thrombosis [Type 4b], stent restenosis [Type 4c]), or Type 5 (MI related to CABG), consistent with the draft endpoint definitions of the Standardized Data Collection for Cardiovascular Trials Initiative.

Hospitalization for unstable angina needing urgent revascularization

Hospitalization for unstable angina needing urgent revascularization is defined as an unscheduled hospitalization for unstable angina in a subject needing urgent coronary revascularization. The criteria and documentation requirements for this endpoint are defined by the Adjudication Committee Charter and the draft endpoint definitions of the Standardized Data Collection for Cardiovascular Trials Initiative.

Coronary revascularization

Coronary revascularization for the purpose of this study comprises procedures of coronary artery bypass grafting (CABG) or percutaneous coronary intervention (PCI).

Stroke

For the purposes of this study, any stroke is defined as strokes of ischemic or undetermined etiology, including strokes of ischemic etiology that have had subsequent hemorrhagic transformation. Stroke of any etiology will include all of the above and hemorrhagic stroke. Hemorrhagic stroke events will also be reported as a safety endpoint.

Arterial revascularizations

For the purposes of this study, arterial revascularizations will comprise any peripheral artery revascularizations of any type.

Hospitalization for unstable angina

Hospitalization for unstable angina must be qualified as being with or without urgent revascularization. The criteria for the diagnosis of hospitalization for unstable angina include clinical symptoms and ECG or imaging evidence of ischemia, in the absence of evidence of permanent myocardial injury.

Hospitalization for congestive heart failure

The criteria for hospitalization for congestive heart failure include a constellation of symptoms, physical examination findings, laboratory evidence, of heart failure, as well as the institution of heart failure therapy.

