## **12. Cerebral hemorrhage risk**

A prior history of hemorrhagic stroke or lacunar infarct resulting in a stroke (a lacunar infarct which was seen with cerebral imaging is not exclusionary in the absence of a clinical stroke). A prior ischemic stroke which resulted in hemorrhagic transformation is not exclusionary.

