### **Major CV events for safety**

At each periodic review, a flag based on  $p \leq 0.001$  for harm will be used to assess major CV events in bococizumab versus placebo. This flag would signal further examination of all available data by the committee with consideration of altering the conduct or terminating any of the ongoing studies in the bococizumab Phase 3 Clinical Development Program. This flag would be applied to chi-square tests for each study; a Cochran-Mantel-Haenszel (CMH) general association test across all studies; and log-rank tests for the CV outcomes studies, performed separately and in a pooled test with stratification by study.

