6.2. Safety Endpoints

Safety endpoints include investigator reported adverse events, (including Type 1 and 3 hypersensitivity reactions and injection site reactions), serious adverse events, vital signs, examination observations (physical and neurological examinations and cognitive testing), 12-lead ECG recordings, and safety laboratory tests, including hematology, blood chemistry studies (including liver function tests and creatine kinase tests), urinalysis studies, and ADA assessments.

Safety endpoints are collected according to the Schedule of Activities in [Appendix 2](#). All safety observations that occur after the first dose of study medication will be summarized regardless of how long an event occurs after the last dose of study medication. Adverse events on the day of first dose of study medication will be considered to be after the first dose; in the absence of the time of the measurement, all other safety observations on the day of the first dose will be considered before the first dose.

For safety summaries that include a comparison to baseline, baseline and all non-missing measurements after the first dose of study medication will be included in safety analyses regardless of whether or not the subject is on double-blind study medication, except as noted below.

Baseline values

For pulse rate (PR) and blood pressure (BP), the baseline will be the mean of all non-missing measurements taken prior to the first dose of randomized study medication on the last day on or before the first dose of study medication for which there is at least one non-missing value. For all other safety measurements, the baseline value will be the last non-missing value obtained on or before the first dose of randomized study medication.

Vital signs

Vital sign measurements will include PR, systolic and diastolic BP, weight, height, waist circumference and temperature.

At each visit sitting systolic and diastolic PR and BP will be measured in duplicates. The second measurement should be taken after the first measurement, according to the local standard of care. The first and second measurements will be recorded on the Case Report Form and their average (i.e., the arithmetic mean) will serve as the value for that visit. The post-baseline value will be the mean of all non-missing observations taken on the same day for which there is at least one non-missing value.

Clinical laboratory measurements

The following laboratory tests will be collected:

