8.2.3. Analysis of Safety Data

Safety will be assessed through adverse events (including Type 1 and 3 hypersensitivity reactions and injection site adverse events), serious adverse events, vital signs, examination results (physical and neurologic examinations and cognitive testing), 12-lead ECG recordings, and safety laboratory tests including hematology, blood chemistry studies (including liver function tests and creatine kinase tests), urinalysis studies, and ADA assessments. The Safety Analysis Set (SAS) includes all subjects who have received at least one dose of randomized study medication and will be used for all safety analyses, unless otherwise specified. All summaries of safety data will be descriptive only, unless indicated otherwise.

For summaries by visit, observations will be assigned to visits according to the analysis windows in [Table 4](#).

Adverse Events

The Medical Dictionary for Regulatory Activities (MedDRA) will be used to classify all AEs with respect to system organ class and preferred term. AEs, AEs leading to discontinuation from treatment, and SAEs after the first dose of study medication will be tabulated by treatment group. AEs after the first dose of study medication will be summarized without any requirement that the intensity increase after the first dose of study medication. Summaries will also be provided by severity. Summaries by the relationship to study therapy will be presented for AEs and SAEs only.

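### Hemorrhagic stroke is promised as a safety endpoint, but the SAP gives it no adjudicated summary by arm, so an excess could be diluted or scattered, though not invisible.

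*SAP*

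**What the plan says.** Under Stroke, SAP Appendix 1.2 sets two definitions and one commitment:

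- The narrow definition: "For the purposes of this study, any stroke is defined as strokes of ischemic or undetermined etiology". Ischemic strokes with later hemorrhagic transformation stay in.
- The broad definition: "Stroke of any etiology will include all of the above and hemorrhagic stroke".
- The commitment: "Hemorrhagic stroke events will also be reported as a safety endpoint". Protocol Appendix 4 carries the same sentence.

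The same SAP appendix defines cardiovascular death to include "death due to stroke (fatal ischemic stroke or fatal stroke of undetermined etiology), or death due to other cardiovascular causes". Fatal hemorrhagic stroke is not named there.

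SAP 6.2 opens its list with "Safety endpoints include investigator reported adverse events, (including Type 1 and 3 hypersensitivity reactions and injection site reactions), serious adverse events, vital signs" and continues through examinations, ECG and laboratory tests. SAP 8.2.3 opens in the same way: "Safety will be assessed through adverse events (including Type 1 and 3 hypersensitivity reactions and injection site adverse events), serious adverse events, vital signs". Neither names hemorrhagic stroke, and neither do Protocol 2.2.4 and 9.4.

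On monitoring, Protocol Appendix 5 sets a flag at p ≤ 0.001 for harm that "will be used to assess major CV events in bococizumab versus placebo". A second flag, at p ≤ 0.01, covers all-cause death. Exclusion criterion 12 in Protocol 4.2, headed as cerebral hemorrhage risk, bars patients with "A prior history of hemorrhagic stroke or lacunar infarct resulting in a stroke".

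**The concern.** The commitment is worded as an addition to the any-etiology endpoint, yet no listed output is built to meet it. By contrast, SAP 8.2.3 does specify a by-arm tabulation for new diagnoses of diabetes. A reader of the final report would have a pooled stroke hazard ratio and a set of preferred-term counts, but no adjudicated estimate for the one stroke type that the appendix singles out for safety reporting.

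At stake is whether the report can describe hemorrhagic stroke by arm with a rate and an interval. If ischemic stroke falls on bococizumab, that fall can offset a rise in hemorrhagic stroke within the pooled result. The primary result is not affected.

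**Working it through.** The plan states no figure for hemorrhagic stroke, so there is none to reproduce. The check has three parts: trace where a hemorrhagic stroke is counted, size the dilution, and ask what a separate table could show.

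**1. Where a hemorrhagic stroke is counted**

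| Output | Non-fatal | Fatal | Separate and adjudicated? |
|---|---|---|---|
| Primary endpoint; DMC major-CV-event flag | No | Only if classed under other cardiovascular causes | No |
| Any stroke of any etiology (SAP 8.2.2, Table 2) | Yes | Yes | Adjudicated, but pooled |
| AE and SAE tables (SAP 8.2.3) | Yes | Yes | By preferred term, from investigator reports |
| All-cause death; DMC all-cause-death flag | No | Yes | Not by type |
| Causes of death (SAP 8.2.2) | No | Yes | Adjudicated; categories set by the Adjudication Committee Charter |
| Listing of potential secondary events (SAP 8.2.2) | Yes | Yes | Listing of investigator reports only |

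The first row assumes that non-fatal stroke in the composite follows the narrow definition. The appendices do not say so outright, but the existence of a separate any-etiology endpoint supports it.

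Subtracting the any-stroke count from the any-etiology count in each arm gives subjects whose only stroke was hemorrhagic. It misses those who also had an ischemic stroke, and it yields no hazard ratio or interval.

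In the tiered AE analysis, Tier 2 needs 5% of subjects in an arm: 0.05 × 5,500 = 275 subjects with one preferred term. Hemorrhagic stroke would be very unlikely to reach that. Unless it is on the Tier 1 list, which is kept in the Safety Review Plan, it gets counts without a risk difference or interval.

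**2. Dilution in the any-etiology hazard ratio**

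Assumed inputs, none from the documents for these stroke types: ischemic HR 0.75 (borrowed from the design value for the composites in Protocol 9.1), hemorrhagic HR 2.0, and hemorrhagic share f of control-arm strokes of 10% to 20%. For rare events:

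HR(any etiology) ≈ (1 − f) × 0.75 + f × 2.0

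- f = 0.10: 0.675 + 0.200 = 0.875
- f = 0.15: 0.6375 + 0.300 = 0.9375
- f = 0.20: 0.600 + 0.400 = 1.00

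Varying the hazard ratios, with f from 5% to 15%:

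- ischemic 0.75, hemorrhagic 2.0: 0.81 to 0.94
- ischemic 0.75, hemorrhagic 3.0: 0.86 to 1.09
- ischemic 1.0, hemorrhagic 2.0: 1.05 to 1.15

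**3. Chance that each comparison shows the harm**

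Assume S = 50 or 100 placebo strokes of any etiology, and f from 5% to 15%. With D total events, the chance of a significant harm result at two-sided 0.05 is about Φ(√(D/4) × ln HR − 1.96), where D = S × (1 + HR) for the pooled endpoint.

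Example with S = 100, f = 0.10, ischemic HR 0.75 and hemorrhagic HR 2.0:

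- Pooled: HR = 0.875, D = 187.5, giving Φ(6.85 × (−0.134) − 1.96) ≈ 0.002.
- Hemorrhagic only: 10 against 20 events, D = 30, giving Φ(2.74 × 0.693 − 1.96) ≈ 0.475.

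At hemorrhagic HR 2.0 over the whole grid, the pooled chance is about 1% or less with ischemic HR 0.75, and about 4% to 18% with ischemic HR 1.0. The hemorrhagic-only chance is about 16% to 64%. The normal approximation is rough at such small counts.

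**The case against.** The strongest reply is that the commitment is already met. It promises reporting as a safety endpoint; it does not promise adjudication or a hazard ratio. SAP 6.1 has potential endpoint events reported as adverse events as well as adjudicated, and SAP 8.2.3 tabulates all AEs and SAEs after the first dose by arm. The Tier 1 list is open-ended, and hemorrhagic stroke may be on it, which would bring a risk difference, an exact interval and a p-value. This stands in part: the events will appear in safety output, so a reader who inferred that no safety analysis contains them would be wrong. But these are investigator terms that may be spread over several preferred terms, SAP 8.2.3 itself notes that AEs are generally not adjudicated, and the Tier 1 list cannot be seen.

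A reader might also infer that the DMC had no harm flag touching hemorrhagic stroke. The documents do not support that. The all-cause-death flag counts every fatal case, and Protocol 2.2.5 gives the DMC regular unblinded review of endpoint SAEs.

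Nor does exclusion criterion 12 show that the sponsor suspects bococizumab of causing hemorrhage. It restricts who enters; Protocol 1.2.4 names other risks.

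Finally, the dilution figures show a general mechanism under assumed inputs and do not predict this trial's result. That objection stands in full.

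**Conclusion.** The point holds in a limited form. The commitment in both appendices has no dedicated adjudicated analysis behind it, and non-fatal hemorrhagic stroke is outside the primary endpoint and the major-CV-event flag. An excess could be diluted in the pooled stroke result or scattered over preferred terms. It would be going too far to conclude that an excess would pass unseen: the AE and SAE tables, the any-etiology test, the cause-of-death table and the listing all carry some of these events.

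The size, about 0.88 to 1.00 for the any-etiology hazard ratio, rests wholly on the assumed hazard ratios and shares. The conclusion about the missing summary does not depend on them. Two open points rest on documents not supplied: how the Adjudication Committee Charter classes fatal hemorrhagic stroke, and whether the Safety Review Plan lists it as Tier 1. This is a cheap improvement to the final report and no threat to the primary analysis.

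**What to change.** Add adjudicated hemorrhagic stroke, fatal and non-fatal, to SAP 6.2, and specify in 8.2.3 one table by treatment group in the Safety Analysis Set with:

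- number and percent of subjects with an event;
- rate per 100 subject-years with 95% CI, by the method already in SAP 8.1.1.1;
- hazard ratio with 95% CI from the Cox model stratified by geographic region and complete statin intolerance, with the SAP's existing convergence rule and the SAP section 7 censoring (time from first dose).

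Label it descriptive, with no alpha. No change to DMC reports is proposed, because SAP version 2.0 was finalized after the program was discontinued. It also preceded sponsor unblinding, so the table could still have been prespecified at that point.

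The cost is one extra table. Strokes are already adjudicated for the any-etiology endpoint, and the methods are already specified. The downside is few events and a wide interval, so the table would describe the risk without settling it.

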Appendix 2. SCHEDULE OF ACTIVITIES

Visit Schedule/Flowchart:

Study Period	Pre	Scr	Run in period				R	6	7	8	9	10	11	12	13	14	15	16	17	18	19	20	EDC ²⁸ / EOS ²⁹
			2	3	4	5																	
VISITS ¹	0	1	2	3	4	5	6	7	8	9	10	11	12	13	14	15	16	17	18	19	20		
Week ¹	NA	NA	-6	-4	-2	0	4	8	14	26	40	52	70	86	104	122	140	156	174	192	208		
Informed Consents ¹	X	X																					
Contact IRT ²	X	X	X	X	X	X	X	X	X	X	X	X	X	X	X	X	X	X	X	X	X	X	
Med hx/Demog.		X																					
Inclusion/exclusion criteria		X	X		X	X																	
Counseling ³		X	X	X	X	X	X	X	X	X	X	X	X	X	X	X	X	X	X	X	X	X	
Vital signs, T, BP/PR ⁴		X				X	X	X	X	X	X	X	X	X	X	X	X	X	X	X	X	X	
Physical Exam ⁵						X					X				X			X			X	X	
Cognitive assessment ⁶						X					X				X			X			X	X	
12 Lead ECG ⁷						X					X				X			X			X	X	
Laboratory																							
Chemistry Group ⁸		X				X			X	X	X	X	X	X	X	X	X	X	X	X	X	X	
Liver function ⁹		X				X	X	X	X	X	X	X	X	X	X	X	X	X	X	X	X	X	
Creatine kinase ¹⁰		X				X					X				X			X			X	X	
ADA/PK/PCSK9 ¹¹				X		X	X		X		X				X			X			X	X	
Hematology ¹²		X				X					X				X			X			X	X	
Urinalysis ¹³		X				X					X				X			X			X	X	
Pregnancy Test ¹⁴		X				X	X	X	X	X	X	X	X	X	X	X	X	X	X	X	X	X	
Biospecimens ¹⁵						X					X												
Lipid Profile ¹⁶	X			X		X	X	X	X	X	X	X	X	X	X	X	X	X	X	X	X	X	
Special Studies ¹⁷		X				X			X		X												
HbA1c ¹⁸						X					X											X	
Hepatitis ¹⁹		X																				X	
Dispense IP ²⁰			X	X	X	X	X	X	X	X	X	X	X	X	X	X	X	X	X	X	X	X	
Injection in clinic ²⁰			X	X	X	X	X	X	X	X	X	X	X	X	X	X	X	X	X	X	X	X	
Con Med Check ²¹		X	X	X	X	X	X	X	X	X	X	X	X	X	X	X	X	X	X	X	X	X	
Adverse Event/SAE Collection ²²	X	X	X	X	X	X	X	X	X	X	X	X	X	X	X	X	X	X	X	X	X	X	
Potential Endpoint Assessment ²²						X	X	X	X	X	X	X	X	X	X	X	X	X	X	X	X	X	
Compliance Check ²³			X	X	X	X	X	X	X	X	X	X	X	X	X	X	X	X	X	X	X	X	
Contraception Chk. ²⁴		X	X	X	X	X	X	X	X	X	X	X	X	X	X	X	X	X	X	X	X	X	
EQ-5D assessment ²⁵						X			X	X		X			X			X			X	X	
PHQ-2/PHQ-9 ²⁶						X					X				X			X			X	X	
HCRU assessment ²⁷							X	X	X	X	X	X	X	X	X	X	X	X	X	X	X	X	

Key: Pre=pre-screening visit; Scr = screening; R = randomization; EDC = early discontinuation of investigational product; EOS = End of Study/Study Completion; IRT= Interactive Response Technology System; T = temperature; BP=blood pressure; PR=pulse rate; hx= history; ECG=electrocardiogram; ADA/PK/PCSK9=anti-drug antibody/pharmacokinetic; and PCSK9 sampling; IP=investigational product; Con Med=concomitant medication; EQ-5D= EuroQol Group quality of life assessment; HCRU=health care resource utilization; PHQ-2/PHQ-9 = patient health questionnaire for depression; Chk.= check.

Footnotes:

1 Visit Schedule:

Visits should be scheduled by the numbered weeks above.

Subjects should be fasting for at least 10 hours prior to all visits during which fasting blood samples will be collected, with the following exceptions. Unscheduled assessments limited to measures of creatine kinase (CK), liver function tests (including alanine amino transferase [ALT], aspartate amino transferase [AST], alkaline phosphatase, and total and direct bilirubin), hepatitis C polymerase chain reaction (PCR), or pregnancy testing, do not require fasting. At Visit 0, where required, or where pre-clinic visit fasting is not the general practice, subjects will need to return for Visit 0 blood sampling, at a subsequent unscheduled visit, so that 10 hour fasting only takes place after informed consent has been obtained. Subjects are permitted to take concomitant medications, on the morning of a visit, taken as prescribed with water. When a subject has missed a scheduled visit, every attempt should be made to contact him/her, to reschedule the visit, by phone, e-mail, text message, and if necessary, by letter and/or certified mail, in instances where the subject is not responsive to contact attempts.

Informed consent:

The subject should be consented prior to any pre-screening procedures being completed at Visit 0. A study specific informed consent will be obtained at Visit 1, the screening visit if not obtained previously. Some study sites may have alternative informed consent requirements as specified by their institutional review board (IRB)/ethics committee (EC), but the general principle is that informed consent must have been obtained prior to the conduct of any study procedure.

Visit 0, Pre-screening visit:

A pre-screening visit will be conducted to collect data which will help the investigator ascertain if a potential subject qualifies for this study. The subject should be consented prior to any pre-screening procedures being completed at Visit 0. At this visit, subjects will have consented to have had lipid levels assessed and provide medical records for review, only, so as to determine if the subject qualifies for this study. At Visit 0, where required, or where pre-clinic visit fasting is not the general practice, subjects will need to return for Visit 0 blood sampling, at a subsequent unscheduled visit, so that 10 hour fasting only takes place after informed consent has been obtained. No data for the subject will be recorded in the pre-randomization visit case report form (CRF) until the cholesterol laboratory results are received, unless the subject experiences an AE or SAE.

The time interval between the Pre-screening Visit (Visit 0) and the Screening Visit (Visit 1) is a maximum of 30 days.

Visit 1:

Visit 1, the screening visit, should be scheduled after the pre-screening data (lipid results and medical records) are available to ascertain eligibility for the study. Study-specific informed consent should be obtained at Visit 1 before all other procedures. Starting at Visit 1, study centers should attempt to schedule each subject's visits at the same time of day, and day of the week for that subject, if possible. Visits should be scheduled based on the week in the Schedule of Activity Table and coordinated with the subject's dosing schedule, so that the visit day is coordinated with a subject's relevant dose day, if possible. Starting at Visit 5 (randomization/baseline visit), and all subsequent visits, if a visit coincides with a scheduled injection of investigational product (IP), the injection should be performed after all other study procedures have been completed.

Lipid, ADA, PK, and PCSK9 testing requirements after randomization:

Lipid (direct LDL-C and lipid panel), ADA, PK, and PCSK9 testing, after randomization, when required, should be scheduled **no sooner than 10 days after the subject's prior dose**, even if this requires an unscheduled visit. If a subject has a visit that is scheduled less than 10 days after the last dose, the visit procedures may take place, but lipid, ADA, PK, and PCSK9 testing should be postponed and performed at the earliest possible time, at an unscheduled visit, no sooner than 10 days after the subject's last dose. A lipid profile will not be collected at EDC/EOS visits. ADA, PK, and PCSK9 samples will be collected at EDC/EOS visits.

Visit windows:

The run-in period is of up to 6 weeks duration, starting at Visit 2, so that there is some flexibility for scheduling the subjects. The run-in visits should take place no less than 7 and no more than 14 days apart. The run-in period continues until Visit 5, randomization. Visit 5 should be scheduled no more than 14 days after Visit 4, the final run-in visit.

After Visit 5, all visits will have a visit window ± 14 days, except for Visits 8 (the Week 14 visit), 11 (the Week 52 visit), both which will have visit window of ± 3 days, and EDC/EOS visits, which will not have visit windows. It will be important to ascertain that the lipid level testing requirement stated above, is met.

Dosing windows:

After randomization, IP dosing windows are 1 day before or up to 4 days after the scheduled dosing date. If more than 4 days after the scheduled day have passed, the subject should skip the dose and resume dosing following the dosing schedule provided by site personnel for the next injection.

Visit 2, start of run-in: Run-in Visit 2 can occur up to 14 days after Visit 1, depending upon the availability of Visit 1 lab results, additional medical records, if they are needed, and the schedule of the subject and clinical site. At Run-in Visit 2, the initiation of the run-in period, the subject will be shown how to self-inject IP (placebo). Only during the run-in period (Visits 2, 3, and 4), subjects will be seen up to two weeks apart (0.5 month periods), to ascertain the subjects' ability to self-inject IP. The other run-in procedures specified in this Schedule of Activities will be adhered to.

Visit sequences: After Visit 5 (Week 0) subjects will be seen at Visit 6 (Week 4), Visit 7 (Week 8), Visit 8 (Week 14), Visit 9 (Week 26), Visit 10 (Week 40), and Visit 11 (Week 52). After Visit 11, subjects will be seen as indicated in the Schedule of Activities. Subjects who discontinue IP early (EDC), will be encouraged to be followed, according to the visit schedule and activities, until study completion (EOS). If the study is not completed by Visit 20, visits will continue every 4 months in accordance with the Schedule of Activities for annual (Visits 11, 14, 17, 20) and interim visits (eg, Visits 12, 13, 15, 16, 18, and 19) until study completion (EOS). The study may end sooner than Visit 20, if the primary endpoint event accrual rate is faster than anticipated or the trial is terminated for other reasons. Subjects who have had an IP dose frequency modification to dosing every 4 weeks, will need to have their visit frequency increased to every 8 weeks, approximately, for the purposes of direct LDL-C measurement and an assessment for adverse events; both serious and non-serious (Protocol Section 6.4.5). If the per-protocol scheduled visit falls within the 8 week window, the scheduled visit will reset the scheduling of the next 8 week direct LDL-C measurement visits.

- 2 IRT: The subjects' visits will be registered at Visit 0 and every visit thereafter, unless they have discontinued treatment with IP.
- 3 Counseling: drug self-injection counseling and therapeutic lifestyle change counseling (diet, exercise) as per NCEP-ATP III or ESC/EAS guidelines or per local medical practice.
- 4 Vital Signs: Vital signs (temperature, pulse rate and blood pressure) shall be recorded at each visit, except for Visits 2, 3, and 4 (unless clinically indicated), as described in Protocol Section 7.2.3.1.
- 5 Physical Exam: Periodic examinations, including a physical exam and basic neurology exam will be performed at baseline (Visit 5), annually, and at the EDC or EOS visit. The physical exam will include the measurement of weight, height and waist circumference at Visit 5 (Protocol Section 7.2.3.2.1). Waist circumference will also be measured at EOS or EDC. Whenever a physical exam is performed, it must include the measurement of weight and a basic neurology exam as described in Protocol Section 7.2.3.
- 6 Cognitive Testing: Cognitive testing will be performed in a subset of designated North American (U.S. and Canada) study sites, at baseline (Visit 5), annually, and EDC or EOS visits only as described in Protocol Section 7.2.3.4.
- 7 ECG: Regularly scheduled ECGs are to be recorded locally, anonymized, saved in the study file, and a copy of the ECG should be sent to the study central ECG file for storage. If a subject experiences a nonfatal adjudicated and confirmed CV event after randomization, a new baseline ECG should be performed following the event. It may be done at a regularly scheduled visit if the visit is to occur within that time frame. If not, a new ECG should be performed at an unscheduled study visit.
- 8 Chemistry Group: At indicated visits only: sodium, potassium, chloride, bicarbonate, creatinine, blood urea nitrogen (BUN; serum urea), glucose. All chemistry studies are to be performed by central laboratory.
- 9 Liver function tests: Liver function tests, including ALT, AST, alkaline phosphatase, and total and direct bilirubin, should be performed at the designated visits. Unplanned visits for reassessing liver function test abnormalities may be required (Protocol Section 8.6.2 and Protocol Appendix 8) and do not require fasting.
- 10 Creatine Kinase: Scheduled CK tests are only drawn at screening, baseline, and, annually thereafter. If a subject complains of muscle discomfort at a visit, a CK level should be drawn. If at any time a CK level is $>5X$ the upper limit of normal (ULN), an unscheduled visit should be scheduled for a repeat CK, within 48 hours if possible, with CK fractionation for isozymes (to assess CK-MM and CK-MB) and urine dipstick. Unscheduled measurements of CK do not require fasting. See Protocol Section 7.2.5, Protocol Section 7.6 and Protocol Appendix 7. Prior to obtaining blood for a CK assessment, investigators should enquire about recent intramuscular injections, heavy exercise, or recent musculoskeletal trauma, and defer CK testing until the next visit or repeat testing at an unscheduled visit, no less than 7 days after the IM injection, heavy exercise, or musculoskeletal trauma, so as to avoid spuriously elevated values.
- 11 ADA/PK/PCSK9 sampling: Anti-drug antibody (ADA), bococizumab drug, and PCSK9 blood samples should be collected in all subjects, at the baseline and designated visits as described in Protocol Section 6 For Visit 3, only a PCSK9 sample is needed. No PK or ADA sample is needed at Visit 3. After randomization, if lipid sampling has been postponed to an unscheduled visit, the corresponding ADA/PK/PCSK9 samples should be postponed as well, and collected at the same time as the rescheduled lipid sample collection. ADA, PK, and PCSK9 samples will be collected at EDC/EOS visits.
- 12 Hematology: Complete blood count (CBC) with white blood cell (WBC) and red blood cell (RBC) counts, hemoglobin, hematocrit, WBC differential and platelet count. All hematology studies are to be performed by central laboratory.
- 13 Urinalysis: Dipstick urinalysis will be performed by study site, locally. Details describing what is evaluated in the urinalysis are described in Protocol Section 7.2.1.2, Table 2. At the screening visit a central lab urine albumin/creatinine ratio assessment may be evaluated, in subjects who have had a cardiovascular event more than 5 years prior to screening and in subjects without a prior qualifying cardiovascular event.

- 14 Pregnancy Test: A woman is of childbearing potential if, in the opinion of the investigator, she is biologically capable of having children, with her partner, and is sexually active (Protocol Section 4.1, inclusion criterion 8). For women of childbearing potential, serum pregnancy tests, performed at the central laboratory, and urine pregnancy tests, tested locally, are performed at the screening visit (Visit 1), before IP administration, at the baseline visit (Visit 5), at all visits after randomization, and at the EDC/EOS visit. Subjects who have missed a menstrual period or who show an indeterminate or positive result on the urine test may not further progress in the study until pregnancy is ruled out using further diagnostic testing (eg, a negative quantitative serum pregnancy test conducted at the central laboratory). At all visits, a negative urine pregnancy result is required before the subject may receive the IP. In the case of a positive confirmed pregnancy, the subject will be withdrawn from study medication but may remain in the study. In addition, pregnancy tests will also be done whenever 1 menstrual cycle is missed during the active treatment period (or when potential pregnancy is otherwise suspected). Pregnancy tests may also be repeated as per request of institutional review boards (IRBs)/ethics committees (ECs) or if required by local regulations. Unscheduled visits for pregnancy testing do not require fasting.
- 15 Biospecimens: Banked biospecimen collection will include a 4 mL whole blood specimen at Visit 5, and 10 mL blood samples processed to plasma at Visits 5 and 11, as specified in Protocol Section 7.5.
- 16 Lipid profile: The fasting lipid profile includes total cholesterol, high density lipoprotein cholesterol (HDL-C), low density lipoprotein cholesterol (LDL-C), very low density lipoprotein cholesterol (VLDL-C), remnant lipoprotein cholesterol (RLP-C), and triglycerides, performed by a central laboratory. After randomization lipid level tests should be scheduled no sooner than 10 days after the subject's prior dose, even if this requires an unscheduled visit. If a subject has a visit that is scheduled less than 10 days after the last dose, the visit procedures may take place, but lipid testing should be postponed and performed at the earliest possible time, at an unscheduled visit, no sooner than 10 days after the subject's last dose. Subjects who have had an IP dose frequency modification to dosing every 4 weeks, will need to have their visit frequency increased to every 8 weeks, approximately, for the purposes of direct LDL-C measurement. A lipid profile will not be collected at EDC/EOS visits.
- 17 Special Lipid and Efficacy Assessments: At the screening visit hs-CRP and Lp(a), and may be evaluated, in subjects who have had a cardiovascular event more than 5 years prior to screening and in subjects without a prior qualifying cardiovascular event. Apolipoprotein (apo) B and apo A-I will not be collected at the screening visit. Special lipid and efficacy blood samples will be collected in all subjects, at Visits 5, 8, and 11, for apo B, apo A-I, Lp(a), and hs-CRP, as described in Protocol Section 6, and measured by a central laboratory.
- 18 HbA1c: HbA1c will be collected, for all subjects, at baseline, Visit 11, and EDC/EOS. HbA1c may be collected at any time, at an unscheduled visit, if necessary for additional safety assessments, as determined by the investigator.
- 19 Viral hepatitis serologies. Hepatitis B and hepatitis C virus screening serologies will be collected at Visit 1 in all subjects and evaluated as per Protocol Appendix 3. Hepatitis C virus serologies will be collected at the EDC/EOS visit, only for subjects from study sites in Canada. A positive or indeterminate hepatitis C serology may trigger a hepatitis C polymerase chain reaction (PCR) test for confirmation. Unscheduled visits for hepatitis C PCR testing do not require fasting.
- 20 Dispense investigational product: IP will be dispensed as designated in the table. During the run-in period (Visits 2, 3, and 4) subjects will self-administer or be administered study drug by a caregiver, during the study visit. At Visit 5, Subjects will be observed during injection of IP, either by self-injection, or as performed by a care giver and observed for a period of 30 minutes, to determine if any signs or symptoms develop. The observation period may be extended, if any signs or symptoms become apparent. After Visit 5, the randomization visit, study sites should try to coordinate the visit schedule with the subject's dosing schedule, when possible. After study procedures are completed, at each visit, subjects should self-inject IP only after blood samples have been collected and the physical exam has been performed.
- 21 Con Med Check: Concomitant medication assessment, including assessment of background lipid lowering medication (see Protocol Section 5.8).

- 22 Adverse events and Potential Endpoint Assessments: Adverse events (AEs) will be reported at every visit. Serious adverse events (SAEs) will be reported from the time of informed consent (see Protocol Section 8.2). Potential disease-related efficacy endpoint assessment will be done at every visit after randomization.
- 23 Compliance Check: The subject's compliance with IP administration, as described in Protocol Section 5.3 will be assessed. After the randomization visit, subjects will be directed to bring any used and unused syringe cartons to each visit. Used syringes will be returned to the study center in a biohazards container, as needed. Compliance with lifestyle guidelines should be reviewed (Protocol Section 4.4) and recorded in the CRF.
- 24 Contraception Check: At these visits, a contraception check should be made for male and female subjects, who, with their partner(s), are of childbearing potential (Protocol Section 4.4.2).
- 25 Health-Related Quality of Life Assessment: EuroQol Group quality of life (EQ-5D) assessments (Protocol Section 7.3.1) at visits 5, 8, 9, 11, 14, 17, 20, and EDC or EOS.
